#### 5.4 STRATEGIES FOR RECRUITMENT AND RETENTION

Subjects will receive compensation for completion of the 30, 90, and 180-day visits. This small stipend will be outlined in the site specific ICF and approved by the IRB prior to subject enrollment.

#### 5.5 PARTICIPANT WITHDRAWAL OR TERMINATION

##### 5.5.1 REASONS FOR WITHDRAWAL OR TERMINATION

All subjects have the right to withdraw at any point during the study without prejudice. The investigator can discontinue any subject, at any time, if medically necessary. Subjects must be discontinued from the investigation by the investigator at any time for any of the following reasons:

- Withdrawal of informed consent.
- Any AEs for which treatment continuation would constitute an unacceptably high risk for the subject.

##### 5.5.2 HANDLING OF WITHDRAWALS OR TERMINATION

The subject must undergo the recommended follow-up assessments specified for the last study visit unless contraindicated due to a medical condition. Withdrawn subjects who have been treated will not be replaced.

Subjects who are discontinued from the study due to an AE(s) will be treated according to standard clinical practice and this protocol and will be followed-up until the final study visit/safety visit as described in **Section 7.3**. All pertinent information concerning the AE will be documented on the appropriate study specific CRF.

A subject may discontinue from the study at any time without any penalty or loss of benefits to which the subject is otherwise entitled. An Investigator may also discontinue a subject from the study without the subject's consent, if the Investigator feels it is in the best medical interest of the subject. The date and the reason for study withdrawal will be indicated on the Study Exit CRF.

#### 5.6 PREMATURE TERMINATION OR SUSPENSION OF THE STUDY OR A STUDY SITE

The study or a study site can be prematurely terminated or suspended by the sponsor. Reasons for termination of the study or a study site may include, but are not limited to, the following:

- Subject enrollment is unsatisfactory.

- The risks and benefits of continuing the study have been reassessed, and the risks outweigh any potential benefits.
- The incidence of AEs constitutes a potential health hazard to the subjects.
- New scientific data do not justify a continuation of the study.
- The investigator or study site exhibit serious and/or persistent non-adherence to the protocol, the Declaration of Helsinki, EN ISO 14155, and/or applicable regulatory requirements.
- The sponsor decides to terminate the study at any time for any other reason.

Furthermore, the study may be prematurely ended if the regulatory authority or the IRB has decided to terminate or suspend approval for the study, the study site, or the investigator.

If the study is prematurely terminated or suspended for any reason, the investigator must inform the subjects and assure appropriate follow-up treatment. Within the timeframes noted in applicable regulations, the sponsor will promptly inform the investigators, study sites, the IRB, and regulatory authorities of the termination or suspension of the study, as well as provide reasons for the action.

## 6. STUDY DEVICE

Cleared devices (K191542) shipped for use in clinical investigations conform to the applicable general safety and performance requirements (GSPR) apart from the aspects covered by the clinical investigation and that, with regard to those aspects, every precaution is taken to protect the health and safety of the subjects. This includes, where appropriate, technical, and biological safety testing and pre-clinical evaluation as well as provisions in the field of occupational safety and accident prevention and taking into consideration the state of the art. Apyx Medical will provide devices for use in this clinical investigation.

### 6.1 PACKAGING & STORAGE

The sponsor will provide appropriate packaging and storage instructions to the study sites.

### 6.2 ACCOUNTABILITY

The investigator, or designee, must maintain an inventory record using the site-specific Device Disposition Form of study devices received, used for treatment, and returned to the Sponsor to ensure that the device will not be dispensed to any person who is not a subject under the terms and conditions set forth in this protocol. There will be 100% accountability for all devices. The clinical study site shall maintain all devices received for clinical trial use in a locked, limited access cabinet or room until the end of the study unless they are returned to Apyx while the study is being conducted, such as at the end of study treatments. Each site will use their existing generators for this study.

### 6.3 DEVICE MALFUNCTION/OBSERVATION

All malfunctions of, or defects of the delivery system will be reported to the Sponsor by the investigational sites. This will include situations where the delivery system did not perform as intended; user errors; study device/component being physically defective, including out of the box failure.

## 7. STUDY PROCEDURES AND SCHEDULE

### 7.1 PRE-PROCEDURE

Study subjects will have verification of eligibility criteria, a brief general examination including medical history, and pre-procedure assessments as detailed below completed within 30 days prior to undergoing the study procedure. In response to the ongoing coronavirus disease (COVID-19) pandemic, preoperative testing can be completed at the Investigator's discretion. Pre-operative testing should be performed as close to the scheduled study procedure as feasible, but in time to get the results.

The following pre-treatment assessments will be performed:

- Subject Gynecomastia Grade will be determined.
- Baseline imaging – frontal, lateral, and oblique views.
- Brief medical history and physical examination per the Investigator's standard of care.
- STPTUP (**Figure 3**).
- STPTIMF (**Figure 4**).
- Bilateral chest measurements (**Table 2**)

Medications that the subject is taking upon entry into the study should also be documented in the Case Report Forms (CRF). All concomitant prescription medications taken during study participation will be recorded on the appropriate study specific CRF. For this protocol, a prescription medication is defined as a medication that can be prescribed only by a properly authorized/licensed clinician. Medications to be reported on the CRF and entered on the eCRF are concomitant prescription medications, over-the-counter medications, and non-prescription medications.

Medication used for analgesia and/or anesthesia should be recorded as concomitant medication as well. To ensure the capture of the foregoing information on pre-existing conditions, sites should also be attentive to the need to document without limitation and whenever discovered: (1) all chronic, episodic or 'as needed' medications used before study enrollment; (2) prior episodic or 'as needed' therapeutic interventions, procedures, or hospitalizations; and (3) recent or planned surgical procedures.

## 7.2 STUDY PROCEDURE

The bilateral gynecomastia surgery and Renuvion APR System use will be as per investigator's standard clinical practice. During the procedure, fat transfer and treatment of the lateral chest and/or axilla is not allowed. The Renuvion APR System will be used on one side only, and alternate consecutively between patients, starting on the right side. For example, subject 001 will be treated with Renuvion on the right side, subject 002, will be treated on the left, subject 003 will be treated on the right, etc. This treatment scheme will continue until enrollment has completed at each site. The subjects will be blinded as to which side has been treated with Renuvion.

Procedure data and adverse events will be captured.

Endermology is not allowed post-procedure for the duration of the study.

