## PROTOCOL SYNOPSIS

Protocol Title:	A Pilot Study of the Renuvion APR System when Used as an Adjunct Procedure in Gynecomastia Surgery
Investigational Device:	The Renuvion APR Handpiece (K191542) is a sterile, single use electrosurgical (monopolar) device intended to be used in conjunction with compatible generators for the percutaneous delivery of radiofrequency energy and/or helium plasma for cutting, coagulation and ablation of soft tissue. The Renuvion APR Handpiece is compatible with the Electrosurgical Generators BVX-200H/P (K170188), and APYX-JS3/RS3 (K192867) owned by Apyx Medical that are indicated for delivery of radiofrequency energy and/or helium gas plasma to cut, coagulate, and ablate soft tissue during open and laparoscopic surgical procedures.
Development Phase:	Pilot
Study Purpose:	To evaluate the use and safety of the Renuvion APR System as an adjunct procedure to bilateral gynecomastia surgery.
Brief Study Overview:	
This is a prospective, multi-center, single-blinded, randomized study of up to 10 study subjects undergoing bilateral gynecomastia surgery with Renuvion APR System used as an adjunct procedure on one side. The study will be conducted at up to 3 investigational centers in the United States.
 
At baseline, the grade of gynecomastia will be recorded by side, male chest measurements will be taken, and pre-surgery photographs taken in the frontal, lateral, and oblique views.
 
The gynecomastia surgery and Renuvion APR System use will be as per investigator's standard clinical practice. During the procedure, fat transfer and treatment of the lateral chest and/or axilla is not allowed. The Renuvion APR System will be used on one side only. The treated side will be randomized and the patient will be blinded as to which side of the chest received Renuvion. Procedure data and adverse events will be captured. Endermology is not allowed post-procedure. Post-procedure compression will be used for 2-3 weeks with a standard compression vest for all subjects.
 
Follow-up images, grade of gynecomastia, and male chest measurements will be taken at D30/D90/D180.
 
All images will be assessed for correct identification of Renuvion-treated side by blinded Independent Photographic Reviewers (IPR) following the D180 visit.
 
Following study participation, the subject will be offered an optional balancing treatment to the side not previously treated with Renuvion.

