Understanding these heat effects of RF energy on cells and tissue can allow the predictable changes to be used to accomplish beneficial therapeutic results. Protein denaturation leading to soft tissue coagulation is one of the most versatile and widely utilized tissue effects. Protein denaturation is the process in which hydrothermal bonds (crosslinks) between protein molecules, such as collagen, are instantaneously broken and then quickly reformed as tissue cools. This process leads to the formation of uniform clumps of protein typically called coagulum through a subsequent process known as coagulation. In the process of coagulation, cellular proteins are altered but not destroyed and form protein bonds that create homogenous, gelatinous structures. The resulting tissue effect of coagulation is extremely useful and most commonly used for occluding blood vessels and causing hemostasis.

In addition to causing hemostasis, coagulation results in predictable contraction of soft tissue. Collagen is one of the main proteins found in human skin and connective tissue. The coagulation/denaturation temperature of collagen is conventionally stated to be 66.8°C, although this can vary for different tissue types. Once denatured, collagen rapidly contracts as fibers shrink to one-third of their overall length. This principal of thermally-induced contraction of collagen through denaturation and coagulation of soft tissue is well known in medicine and is used to achieve beneficial results in ophthalmology, orthopedic applications, and the treatment of varicose veins. Once tissue is heated to the appropriate temperature, protein denaturation and collagen contraction occur resulting in a reduction of volume and surface area of the heated tissue. Noninvasive use of RF devices, lasers, and plasma devices have been used for the reduction of facial wrinkles and rhytides caused by thermal-induced collagen/tissue contraction since the mid-1990s.

Recently, the use of thermal-induced collagen/tissue contraction has been expanded to minimally invasive procedures. Laser-assisted lipolysis (LAL) and radiofrequency-assisted lipolysis (RFAL) devices have combined the removal of subcutaneous fat with soft tissue heating to address the skin laxity that often results from fat volume

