### 2.2.2 POTENTIAL BENEFITS

This study is being conducted to determine if there is a possible benefit of using the Renuvion APR device as an adjunct procedure to Gynecomastia surgery.

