##### **4.3.2 ADDITIONAL ENDPOINTS**

Other additional endpoints for this study are as follows:

1. Bilateral analysis of change to STPTUP (Tebbetts & Adams High 5 Measurements) from baseline to day 30, 90, and 180.
2. Bilateral analysis of change to STPTIMF (Tebbetts & Adams High 5 Measurements) from baseline to day 30, 90, and 180.
3. Bilateral analysis of male chest measurements (Murphy) from baseline to day 30, 90, and 180.
4. Bilateral analysis of skin excised during the procedure by Gynecomastia Grade (Rohrich Classification).
5. Bilateral analysis of gland tissue removal methods (Longheu) during the procedure by Gynecomastia Grade.
6. The Principal Investigator, sub-investigator or qualified clinician delegated by the principal investigator, will complete a bilateral PGAIS assessing overall aesthetic improvement in the treatment area at day 30, 90, and 180 post-treatment.
7. The subject will complete a bilateral SGAIS assessing overall aesthetic improvement in the treatment area at day 30, 90, and 180 post-treatment.
8. The subject will complete a bilateral Patient Satisfaction Questionnaire (PSQ) at the 180-day follow-up visit.

9. Baseline images compared to Day 30, 90, and 180 images will be assessed for correct identification of Renuvion-treated side by blinded IPRs.

[figure not shown]

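### The surgeon can know the Renuvion side before operating and nothing keeps the base surgery comparable between sides, so the side-to-side effectiveness contrasts can be confounded

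*Protocol*

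**What the plan says.** On the operation, Protocol section 7.2 says: "The bilateral gynecomastia surgery and Renuvion APR System use will be as per investigator's standard clinical practice". It forbids fat transfer and work on the lateral chest or axilla, but sets no rule that the two sides be operated on alike.

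On the side, section 7.2 says: "The Renuvion APR System will be used on one side only, and alternate consecutively between patients, starting on the right side". It then illustrates: "For example, subject 001 will be treated with Renuvion on the right side", with the next subject on the left, and so on. The synopsis differs: "The treated side will be randomized and the patient will be blinded as to which side of the chest received Renuvion". Section 7.4, headed as the randomization section, gives no sequence and no means of concealment.

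Two of the additional endpoints in section 4.3.2 are features of the surgery itself: "Bilateral analysis of skin excised during the procedure by Gynecomastia Grade (Rohrich Classification") and "Bilateral analysis of gland tissue removal methods (Longheu").

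On the aim, section 2.2.2 says: "This study is being conducted to determine if there is a possible benefit of using the Renuvion APR device as an adjunct procedure". Section 3 adds that effectiveness is assessed and that the data may support a later pivotal study.

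**The concern.** A split-chest comparison isolates an adjunct only if both sides receive the same base operation and one side receives the device in addition. Here the person who decides how much to aspirate, how to remove gland and how much skin to excise can know which side will get the device. A surgeon who expects tightening on that side may operate differently there, even without intending to.

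Pinch thickness, sided chest measurements, investigator and subject ratings, the satisfaction questionnaire and the photographs can all respond to what was removed. If removal differs systematically by side, these contrasts no longer answer the question in section 2.2.2. Blinded photographic reviewers and blinded subjects do not remove the problem, because they would be judging a real tissue difference that has another cause.

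**Working it through.** The plan states no effect size, standard deviation or power, so there is no figure to reproduce. The check is mainly of the text.

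**1. Is the side predictable?** Under the alternation in 7.2 it follows from the subject's place in the sequence, so it is known in advance with probability 1. Under a concealed random allocation, a surgeon could only guess, with probability 1/2.

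**2. Who is blinded?** Subjects (synopsis, 7.2, 7.4) and the photographic reviewers (4.3.3.7). Nothing conceals the side from the surgeon.

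**3. What limits unequal surgery?**
- Sections 5.2 and 5.3 require symmetrical Rohrich grades and chest measurements within 3%. This balances anatomy before surgery, not the surgery.
- Section 7.2 bars fat transfer and lateral chest or axilla treatment. Liposuction, gland removal and excision stay free.
- Section 7.3.1 gives every subject the same compression vest. This concerns aftercare.
- Endpoints 4 and 5 analyse excision and gland-removal method by side. This can reveal some imbalance but does not prevent it.
- Section 7.2 says procedure data are captured, without naming liposuction volume by side.

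**4. Which contrasts are exposed?** Endpoints 1–3 and 6–9 can be confounded by differences in the base surgery. Endpoints 4 and 5 are different in kind: they are surgical decisions, open to direct influence by knowledge of the side.

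**5. Direction.** Let b_i be the shift in a measurement in subject i (device side minus other side) that is due to unequal surgery. The mean contrast moves by (1/n) Σ b_i. Differences in random directions tend to cancel; only differences that tend to follow the device side bias the mean. The document gives no value for any b_i, so no shift in millimetres can be stated.

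**6. Illustration on the photographic rule (4.3.3.7).** Success is a correct choice by at least 2 of 3 reviewers. Assume no device effect, and let p be the probability that unequal surgery alone leads a reviewer to pick the device side. Assume reviewers and subjects are independent, with n = 10 (section 10.2). Then s = 3p²(1 − p) + p³, the expected number of successes is 10s, and P(at least 8 of 10) is the upper binomial tail with probability s.

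| p (assumed) | s | Expected of 10 | P(at least 8 of 10) |
|---|---|---|---|
| 0.5 | 0.500 | 5.0 | 0.055 |
| 0.6 | 0.648 | 6.5 | 0.26 |
| 0.7 | 0.784 | 7.8 | 0.63 |
| 0.8 | 0.896 | 9.0 | 0.92 |

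For p = 0.7: 3 × 0.49 × 0.3 + 0.343 = 0.441 + 0.343 = 0.784. The cut of 8 of 10 is chosen here for display and is not a rule of the plan. Reviewers look at the same tissue, so positive correlation between them is likely and would pull s towards p.

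**The case against.** The case on the other side has weight. This is a descriptive pilot of up to 10 subjects whose only primary endpoint is adverse events. Each subject is his own control, anatomy must be symmetrical at entry, several procedures are barred, and two key surgical features are analysed by side. Alternation also roughly balances right and left (5 and 5 in a single run of 10; 6 and 4 if it restarts on the right at sites of 4, 3 and 3), so ordinary operative asymmetry tends to cancel. All of this stands. It lowers the risk, but does not address surgery that differs because the side is known.

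Three stronger readings are tempting and are not supported:

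- A reader might infer that every side difference mixes device and surgery. The text permits unequal surgery; it does not show that it occurs. Section 8.2.2 treats burns and gas buildup as device related. Upper-pole pinch thickness is taken above the breast parenchyma (4.3.3.1), so gland removal is not its direct determinant.
- A reader might infer that a difference in gland-removal method cannot be a device effect because heating follows removal. The background sentence that invites this says that devices "have combined the removal of subcutaneous fat with soft tissue heating to address the skin laxity that often results from fat volume" removal, but it describes laser- and radiofrequency-assisted lipolysis devices and gives no sequence for Renuvion. Less excision may equally be part of what the adjunct achieves.
- A reader might put a figure in millimetres on the bias. That would rest wholly on assumed inputs and on all differences running in the same direction.

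It is also fair to say that displays with and without certain subjects are usually left to an analysis plan. Concealing the side and recording the surgery are not: no later analysis can supply them.

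**Conclusion.** The concern holds in a limited form. The surgeon can know the device side beforehand, and no provision keeps the base surgery comparable, so endpoints 1–3 and 6–9 can be confounded and endpoints 4 and 5 can be influenced. Whether this happens, and by how much, cannot be determined from the document. The photographic figures show only that a systematic imbalance could look like a device effect, given the assumed p and independence.

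The point does not touch device-specific adverse events and does not invalidate the pilot. It is a worthwhile, low-cost improvement, because section 2.2.2 makes a possible benefit the question and section 3 looks ahead to a pivotal study. Randomizing the side is necessary but not sufficient: an allocation that is random yet known before the operation leaves the same opening.

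**What to change.** 1. Reconcile section 7.2 with the synopsis by replacing alternation with a concealed random allocation of the side, and describe it in section 7.4. Delayed disclosure conceals nothing while alternation stands.
2. In section 7.2, have the planned gland-removal method and planned skin excision recorded per side before the allocation is opened. Open it (for example, a sealed envelope) just before the device is used, as late in the operation as the investigator's own practice allows. Any step after opening is still taken with the side known, and the recorded plan then makes departures visible.
3. Record the actual gland-removal method, excised skin and aspirate volume per side. Show the descriptive side contrasts with and without subjects whose base surgery differed between sides, with the meaning of differed fixed before the data are seen. This is a check on robustness and does not restore comparability.

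Cost: a paragraph in 7.2, a few case report form fields, someone to hold the allocation, one extra table row, and slightly later set-up of the handpiece for a side. Operative technique and order stay with the investigator.

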Number of Sites Enrolling Participants:	Subjects will be recruited from up to 3 study sites in the US.
Sample Size:	N = Up to 10 treated subjects; subjects enrolled may be greater than subjects treated.
Subject Population:	Healthy, male adult subjects, ages 18 – 75 years old who meet the inclusion/exclusion criteria.
Inclusion Criteria:	
 
1. Male subjects, ages 18 – 75 years old.
 
2. ASA Physical Status Classification System Class I and Class II subjects.
 
3. Clinical diagnosis of primary or secondary Gynecomastia.
 

	
 
4. Gynecomastia Rohrich Grade IIA or higher.
 
5. Symmetrical gynecomastia Rohrich grades.
 
6. Symmetrical chest measurements (no more than 3% variance between sides).
 
7. Scheduled for Gynecomastia surgery.
 
8. Willing to have Renuvion APR System as an adjunct procedure on one side understanding that an optional balancing procedure may be provided post-study exit.
 
9. Understands and accepts the obligation not to undergo any other procedures or treatments in the areas to be treated during study participation.
 
10. Absence of physical conditions unacceptable to the investigator.
 
11. Willing and able to comply with protocol requirements, including study-required images/photos, assessments/measurements, and returning for follow-up visits.
 
12. Willing to release rights for the use of study photos, including in publication.
 
13. Able to read, understand, sign, and date the informed consent.
 

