### **4. STUDY DESIGN AND ENDPOINTS**

#### **4.1 DESCRIPTION OF THE STUDY DESIGN**

This study is a prospective, multi-center, single-blinded, randomized pilot clinical trial to be conducted at up to 3 clinical site(s). Up to 10 subjects will be enrolled and treated if they meet the inclusion/exclusion criteria and provide written informed consent. A higher number of subjects than 10 may be enrolled due to screen failures or withdrawal of consent.

Subjects meeting all entrance criteria and confirmed eligible will be enrolled. The gynecomastia surgery and Renuvion APR System will be used as per the Investigator's standard clinical practice. During the procedure, fat transfer and treatment of the lateral chest and/or axilla is not allowed. Subjects will only be treated on one side utilizing the Renuvion APR System. Images will be taken prior to treatment and during each follow-up visit. These images will be assessed for correct identification of the Renuvion-treated side by blinded Independent Photographic Reviewers (IPRs) following the D180 visit. Baseline assessments and pre-treatment images should be obtained within the 30 days prior to study treatment. Endermology is not allowed post-procedure. Post-procedure compression will be used for 2-3 weeks with a standard compression vest for all subjects.

Following study participation, the subject will be offered an optional balancing treatment to the side not previously treated with Renuvion.

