#### 4.3.3.7 INDEPENDENT PHOTOGRAPHIC REVIEW

Three experienced, blinded photographic reviewers will perform a qualitative analysis/review of pre-treatment and post-treatment sets of images for each subject. Images will be provided in a blinded and randomized order. Each blinded reviewer will choose which side of the chest was treated with Renuvion. Success will be correct identification of treated side of the chest by at least 2 of the 3 reviewers.

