### 5.2 INCLUSION CRITERIA

Subjects must meet all the following criteria for study enrollment:

- Male subjects, ages 18 – 75 years old.
- [ASA Physical Status Classification System](#) Class I and Class II subjects.
- Clinical diagnosis of primary Gynecomastia.
- Gynecomastia Rohrich Grade IIA or higher.
- Symmetrical gynecomastia Rohrich grades.
- Symmetrical chest measurements (no more than 3% variance between sides).
- Scheduled for Gynecomastia surgery.
- Willing to have Renuvion APR System as an adjunct procedure on one side understanding that an optional balancing procedure may be provided post-study exit.
- Understands and accepts the obligation not to undergo any other procedures or treatments in the areas to be treated during study participation.
- Absence of physical conditions unacceptable to the investigator.
- Willing and able to comply with protocol requirements, including study-required images/photos, assessments/measurements, and returning for follow-up visits.
- Willing to release rights for the use of study photos, including in publication.
- Able to read, understand, sign, and date the informed consent.

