#### 7.4 SUBJECT RANDOMIZATION AND TREATMENT GROUP ASSIGNMENT

All subjects will be treated per standard of care.). They will be blinded as to which side of the chest is receiving Renuvion.

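### The protocol calls the treated side randomized, but Section 7.2 assigns it by strict alternation starting on the right, so every assignment can be foreseen

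*Protocol*

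**What the plan says.** The Synopsis, under Brief Study Overview, states: "The treated side will be randomized and the patient will be blinded as to which side of the chest received Renuvion". Section 4.1 repeats the design label: "This study is a prospective, multi-center, single-blinded, randomized pilot clinical trial". It does not name the side, but every subject receives the device on exactly one side, so the side is the only thing that could be randomized.

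Section 7.2 gives the rule that sites would follow: "The Renuvion APR System will be used on one side only, and alternate consecutively between patients, starting on the right side". Its example puts subject 001 on the right, 002 on the left and 003 on the right. It then adds: "This treatment scheme will continue until enrollment has completed at each site".

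Section 7.4 is headed as the section on randomization and group assignment. It says that care is standard and, of the subjects, "They will be blinded as to which side of the chest is receiving Renuvion". It gives no sequence, method or concealment. The only other random step in the protocol is the order in which images are shown to the photographic reviewers (Section 4.3.3.7), which does not assign a side.

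**The concern.** A site cannot both randomize the side and alternate it. The sections need to agree, because as they stand the results would be reported as randomized when they were not. The data may also support a later pivotal study (Section 3).

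Most additional endpoints set the two sides of the same chest against each other. The adverse-event endpoint is recorded for both sides, which invites the same comparison. The choice of side is therefore the allocation. If it is known in advance, it can influence:

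- the order in which patients are taken;
- borderline calls on the entry criterion "Symmetrical chest measurements (no more than 3% variance between sides";
- baseline caliper and chest readings;
- operative planning.

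Blinding is a lesser and conditional risk. A subject or photographic reviewer who learned both the scheme and the subject number could work out the side. The protocol does not say that either is told.

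The rule also leaves gaps. It can be read as running per site or across the study. It refers both to consecutive patients and to subject numbers, and these can diverge because the Synopsis allows "N = Up to 10 treated subjects; subjects enrolled may be greater than subjects treated".

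**Working it through.** The protocol states no figure for allocation that could be reproduced. The inputs are the Section 7.2 rule, up to 10 treated subjects and up to 3 sites (Section 10.2), and the two-of-three reviewer rule (Section 4.3.3.7).

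**Predictability over 10 treated subjects**

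| Scheme | Possible sequences | Expected correct guesses |
|---|---|---|
| Section 7.2 (R, L, R, L, …) | 1 | 10 |
| Simple randomization | 2^10 = 1,024 | 10 × 0.5 = 5.0 |
| 5:5 random list, composition known and past sides seen | C(10,5) = 252 | 5 + (1024/252 − 1)/2 = 6.53 |

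Under simple randomization the chance of guessing all ten sides is 0.5^10 = 0.00098.

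**Per site or study-wide.** Study-wide alternation gives 5:5 right to left. If each site restarts on the right, a site with an odd count treats one more on the right. Ten subjects over up to three sites then give 5:5 (no odd site) or 6:4 (two odd sites). Nine subjects split 3/3/3 give 6:3. The side is foreseeable under either reading.

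**Subject number or order of treatment.** Assume that one screen failure keeps its number; the protocol does not say. If it holds number k (1 to 10), every later treated subject's number is one ahead of his treatment order. The two readings then give opposite sides for 11 − k of the ten treated subjects: 10 for k = 1, 9 for k = 2, and 1 for k = 10.

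**Illustration of order selection (assumptions, not data).** Let the baseline right-to-left difference be uniform on ±w%. Suppose two patients wait together and staff always order them to favour the same arm.

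- The expected shift for the pair is E|d1 − d2| = 2w/3.
- One such pair moves the ten-subject mean by (2w/3)/10, which is 0.07 points at w = 1 and 0.2 at w = 3.
- Five pairs, the extreme case, move it by 0.33 to 1.0 points. The expected shift under randomization is 0.
- A 4/3/3 split with alternation per site has only 2 + 1 + 1 = 4 complete pairs, so five is then out of reach.
- Change-from-baseline endpoints would not carry these shifts over one-for-one.

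**Reviewer rule.** The task is: "Each blinded reviewer will choose which side of the chest was treated with Renuvion". If all three guess, the chance that at least two are right is 3 × 0.5^3 + 0.5^3 = 0.50. If one reviewer knew the side and two guessed, it would be 1 − 0.25 = 0.75. If two knew, it would be 1.00. This matters only if the number and the scheme reach a reviewer.

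**The case against.** The strongest counter-argument is that little harm follows. This is a descriptive pilot of up to 10 subjects. Each is his own control, with equal gynecomastia grades on both sides and chest measurements within 3%. The usual damage from alternation, different kinds of patient in the two arms, cannot arise. No section blinds the investigator, so knowledge of the side could affect surgery and the investigator's aesthetic ratings even under concealed randomization. Alternation also protects balance: with simple randomization of ten subjects, a split of 8:2 or worse has probability 2 × (1 + 10 + 45)/1024 = 10.9%.

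Much of this stands. It limits the likely bias, makes the order-selection figures illustrative only, and means that dropping the randomized label is a legitimate repair. It is also fair that only the Synopsis names the side as randomized, that a stray bracket in Section 7.4 may point to lost text, and that Section 7.2 can be read as following treated patients with the numbers as mere examples.

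None of this removes the conflict. Section 7.2 is complete in itself and contradicts the Synopsis whatever Section 7.4 once contained. The within-subject design does not make a fixed sequence random, and it does not prevent the side from being foreseen when symmetry is judged and baseline is measured.

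**Conclusion.** The point holds and must be fixed. The protocol contradicts itself on its only allocation step, and under the rule that sites would follow all 10 of 10 sides are foreseeable. This conclusion needs no assumption beyond the text of the Synopsis and Sections 4.1, 7.2 and 7.4.

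The size of any bias in the results cannot be derived from the protocol and may be small. The order-selection, screen-failure and reviewer figures each depend on the assumptions stated with them. The certain consequence is that an alternating allocation would be reported as randomized; the gaps in the rule add that sites could assign opposite sides while each believed it was following Section 7.2.

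**What to change.** Choose one of two repairs and align the Synopsis and Sections 4.1, 7.2 and 7.4 with it.

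1. **Randomize.** Replace the alternation text in Section 7.2 and complete Section 7.4. Take the side from a centrally held, computer-generated list indexed by treated subject, using either simple randomization or a balanced list whose composition is not disclosed to sites. Release each side only after eligibility, baseline measurements and baseline photographs have been recorded. If right-left balance matters, the balanced list avoids the 10.9% risk of a split of 8:2 or worse.
2. **Keep alternation.** Remove the word randomized from the Synopsis and Section 4.1 and retitle Section 7.4. State whether the sequence runs per site or study-wide, and whether it follows subject number or order of treatment. Describe and report the allocation as alternating.

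The first option gives the stronger design; the second fully resolves the contradiction but leaves the sides predictable. The cost is protocol wording and, for the first option, a short list held by the sponsor or in the data capture system. Neither needs extra subjects, visits or staff.
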